5.1. Overall Design

This is a single-center, randomized, crossover study assessing the percentage of successful doses, speed, and experience of administering both NG and a commercially available GEK during simulations of severe hypoglycemia emergencies. Participants in the study will administer nasal and injectable glucagon devices to manikins.

Study I8R-MC-IGBM (IGBM) is divided into 2 parts, with different types of participants: Part A (Trained Users, who will attend all study visits with a PWD) and Part B (Untrained Users). Both parts of the study may be run at the same time.

The study is intended to simulate real-life conditions to capture and document, in a controlled setting, any differences in how Trained Users and Untrained Users use NG and GEK, and their experience of doing so.

5.1.1. Types of Participants

Participants are defined as follows:

- **Trained User:** A participant who, during the study, will be given a level of training intended to mimic that of a real-life caregiver, relative, or close friend of a PWD.
 - “Trained User” participants must be either related to, or a close friend of, a PWD, and therefore already familiar with diabetes and the risk of severe hypoglycemia. Each Trained User must be recruited alongside the PWD with whom they are familiar, as a “dyad” (a pair of people who have a pre-existing relationship).
 - The Trained User will receive instruction on the use of each device, from the PWD, before taking part in the simulation using that device.
 - Trained Users must not have actually administered injectable glucagon (or another rescue medication) in the past. However, they may own a glucagon rescue kit, and may have been instructed in its use, as long as such instruction occurred at least 2 years before screening.
- **PWD:** The PWD who is the close friend or relative of the Trained User.
 - During the study, the PWD will be trained by site staff on the use of each device, and before each simulation, will relay these instructions to the Trained User.
 - The PWD previously may have been instructed in the use of a glucagon rescue kit, as long as such instruction occurred at least 2 years before screening.
- **Untrained User:** A participant who will not be given training during the study on either device, and who has limited knowledge of severe hypoglycemia and how to treat it.
 - These participants are intended to approximate a real-life colleague or acquaintance of a PWD: someone who is aware of the PWD’s condition and is

willing to intervene in an episode of severe hypoglycemia, but has not received instructions. Untrained Users in this study may or may not know a PWD in real life. In any case, they must not have caregiving responsibilities toward a PWD.

- Untrained Users will participate in the study alone (not as part of a dyad).
- Prior to the simulations in this study, Untrained Users will be given basic information about severe hypoglycemia and briefly shown an example of each rescue device.

[figure not shown]
5.1.2. Device Assessment Criteria

The criteria for assessing each device include the following:

- **Dose:** Are Trained Users and Untrained Users able to administer a successful dose more often in an emergency with one device than the other?
- **Speed:** Are Trained Users and Untrained Users able to deliver a dose faster in an emergency with one device than the other?
- **Accuracy:** Do Trained Users and Untrained Users use one device more correctly, i.e. perform the critical steps for dose administration, with fewer errors?
- **Preference:** Overall, do Trained Users, PWDs, and Untrained Users prefer one device over the other?
- **Confidence:** How confident are Trained Users and Untrained Users in their ability to successfully deliver a dose? How confident are PWDs in the ability of Trained Users to successfully deliver a dose?
- **Ease of Use:** How easy do Trained Users and Untrained Users find each device to use? How easy do PWDs think Trained Users find each device?
- **Task Load:** How do Trained Users and Untrained Users rate each simulation in terms of the mental demand, frustration, and other aspects measured using the NASA Task Load Index (TLX)?

Study governance considerations are described in detail in [Appendix 2](#).

[figure not shown]
[Figure IGBM.1](#) (Part A) and [Figure IGBM.2](#) (Part B) illustrate the study design.

Abbreviations: GEK = glucagon emergency kit; NASA = National Aeronautics and Space Administration; NG = nasal glucagon; PWD = person with diabetes; TLX = Task Load Index.

Figure IGBM.1.

Illustration of study design for Protocol I8R-MC-IGBM: Part A.

Abbreviations: GEK = glucagon emergency kit; NASA = National Aeronautics and Space Administration; NG = nasal glucagon; TLX = Task Load Index.

Figure IGBM.2. Illustration of study design for Protocol I8R-MC-IGBM: Part B.

5.1.3. Detailed Description of Study Procedures

As shown in [Figure IGBM.1](#) and [Figure IGBM.2](#), study procedures will vary between Part A (Trained Users) and Part B (Untrained Users).

Details of each simulation are intended to be included in a study operations manual. Site staff will make a video recording of each simulation, for study participants to review later, before they complete questionnaires. The videos may also be used to validate the site's evaluation of critical steps and other aspects of the simulation.

5.1.3.1. Part A (Trained Users)

Trained Users will be required to attend the study site on 3 occasions, each time accompanied by the PWD with whom they are associated.

At **Visit 1**, each Trained User and their associated PWD will be evaluated for eligibility, give informed consent, and be randomized to 1 of 2 schedules ([Table IGBM.2](#)).

Randomization will be stratified by the type of diabetes, i.e. randomization will be performed separately for PWDs with type 1 diabetes mellitus (T1DM) and type 2 diabetes mellitus (T2DM), and their accompanying Trained User.

Following randomization, site staff will instruct the PWD how to use Device 1 (i.e. either NG or GEK, depending on the randomization). This instruction will include a mock administration, during which the PWD will actuate the device. After a "memory decay" period including a distractor task (see Section [5.1.3.5](#)), the PWD will relay instructions on how to use Device 1 to the Trained User.

At **Visit 2**, approximately 7 days after Visit 1, each Trained User will take part in a simulation of a severe hypoglycemia emergency with a manikin (see Section [5.1.3.3](#)). The gender of the manikin will match the gender of the PWD. The PWD will not be in the room and will not observe the simulation. Site staff will assess dose administration (successful/unsuccessful; see Section [5.1.3.4](#)), and the time taken to administer a dose.

After a short rest period, the Trained User will complete the NASA TLX questionnaire about their experience with Device 1. At around the same time, site staff will instruct the PWD how to use Device 2. After a "memory decay" period including a distractor task (see Section [5.1.3.5](#)), the PWD will relay instructions on how to use Device 2 to the Trained User.

At **Visit 3**, approximately 7 days after Visit 2, each Trained User will take part in a second simulation, similar to the first. They will be asked to treat the manikin with Device 2, again observed by site staff only. The gender of the manikin will again match the gender of the PWD. After a short rest period, the Trained User will complete the NASA TLX questionnaire about their experience with Device 2. At around the same time, site staff will assemble a video of both simulations (from Visits 2 and 3). Then both PWD and Trained User will watch the video. After a delay of 55 to 60 minutes, the PWD and Trained User will each complete a questionnaire comparing both devices; later they will complete individual questionnaires for both NG and GEK, in randomized order ([Table IGBM.2](#)). Details of the questionnaires are in Section [9.10](#).

Participants will be given a device-specific questionnaire only if the Trained User attempted to administer that device. For example, there will be no questionnaire for a simulation if insulin was wrongly administered instead of the glucagon device, or if no attempt was made to administer a device. Similarly, participants will be given the comparative questionnaire only if the Trained User attempted to administer both NG and GEK during the respective simulations.

5.1.3.2. Part B (Untrained Users)

Untrained Users will attend the site for 2 visits ([Figure IGBM.2](#)).

At **Visit 1**, after being evaluated for eligibility and giving informed consent, each Untrained User will be randomized to 1 of 2 schedules ([Table IGBM.2](#)), which will determine the device used at each simulation. Male manikins will be used in each case.

Each Untrained User will be given a brief explanation of diabetes and severe hypoglycemia, and briefly shown an example of Device 1 (NG or GEK depending on randomization). No instruction will be given on how to use the device; nor will the Untrained User be allowed time to read any instructions for using the device.

Each Untrained User will then take part in a simulation (see Section [5.1.3.3](#)) using Device 1. Staff will assess successful or unsuccessful treatment (Section [5.1.3.4](#)), and time to successful administration (if this occurred within the allotted time). After a short rest period, the Untrained User will complete the NASA TLX questionnaire about their experience.

At **Visit 2**, approximately 7 days after Visit 1, each Untrained User will be shown an example of Device 2. As at Visit 1, no instruction will be given on how to use the device. The Untrained User will take part in a simulation using Device 2, and then complete the NASA TLX. Site staff will assemble a video of both simulations, and the Untrained User will watch it. After a delay of 55 to 60 minutes, the Untrained User will fill in a questionnaire comparing both devices, and then individual-device questionnaires in randomized order ([Table IGBM.2](#)). Details of the questionnaires are in Section [9.10](#). The Untrained User will be given a device-specific questionnaire only if they attempted to administer that device. For example, there will be no questionnaire for a simulation if insulin was wrongly administered instead of the glucagon device, or if no attempt was made to administer a device. Similarly, Untrained Users will be given the comparative questionnaire only if they attempted to administer both NG and GEK devices during the respective simulations.

5.1.3.3. Example Simulation

The participant in the simulation (Trained User or Untrained User) will be taken into a room where a fully clothed adult manikin is present (e.g. lying face-up on the ground, on a bed, or in a chair). The participant will be told that the manikin represents a PWD experiencing severe hypoglycemia. For Part A, site staff will refer to the manikin using the PWD's name during the simulation.

Near to the manikin will be a backpack, chest of drawers, or other receptacle, appropriate to the simulated location (bedroom, office, etc.). This will contain diabetes supplies (glucometer and

strips, alcohol swabs, lancing device, insulin syringe and a vial of insulin) and the glucagon device (NG or GEK depending on randomization); it may also contain other everyday items.

The participant will be told to find the PWD's glucagon device and administer rescue glucagon as quickly as possible. Once the participant finds the device, the timing of the simulation will start. While the participant attempts to administer glucagon, site staff will emphasize the urgency of the situation, e.g. by telling the participant that it will be some time before an ambulance arrives. Distracting sounds and events will be incorporated to simulate the stress of a real-life situation. After approximately 15 minutes, site staff will tell the participant that the ambulance has arrived, ending the simulation.

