3.2. Background

Hypoglycemia, one of the most serious acute complications of diabetes treatment, is defined as an abnormally low blood glucose level that exposes the individual to potential harm. The use of glucagon is indicated for the treatment of hypoglycemia in people unable or unwilling to consume carbohydrates by mouth, according to American Diabetes Association (ADA) guidance (ADA 2018). ADA guidance identifies a 3-stage classification of hypoglycemia:

Level	Glycemic criteria	Description
Hypoglycemia alert value (level 1)	≤ 70 mg/dL (3.9 mmol/L)	Sufficiently low for treatment with fast-acting carbohydrate and dose adjustment of glucose-lowering therapy
Clinically significant hypoglycemia (level 2)	≤ 54 mg/dL (3.0 mmol/L)	Sufficiently low to indicate serious, clinically important hypoglycemia
Severe hypoglycemia (level 3)	No specific glucose threshold	Hypoglycemia associated with severe cognitive impairment requiring external assistance for recovery

Source: ADA Standards of Medical Care in Diabetes – 2018.

Based on this classification, the ADA recommends that glucagon should be prescribed for all individuals at increased risk of clinically significant hypoglycemia (level 2), so that glucagon is available should it be needed. Furthermore, an individual does not need to be a healthcare professional to safely administer glucagon.

Nasal glucagon, also known as LY900018, is an investigational drug-device combination product intended for the treatment of severe hypoglycemia (level 3 in the ADA guidance), in adult and pediatric PWDs. Nasal glucagon consists of a single-use nasal dosing device that delivers a fixed 3-mg dose of glucagon powder, absorbed passively through the nasal mucosa.

Nasal glucagon is being developed as an alternative to commercially available GEKs for treatment of severe hypoglycemia, with a needle-free device and fewer steps for administration.

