3.3. Benefit/Risk Assessment

This study does not involve the dosing of study drug to humans. As such, there is no expected benefit to study participants. During each simulation with a GEK, there is a risk that participants may suffer a needle-stick injury, which may also result in accidental administration of the marketed comparator product. Site staff will closely monitor simulations and respond to any such safety issues that arise.

4. Objectives and Endpoints

Table IGBM.1 shows the objectives and endpoints of the study.

Table IGBM.1. Objectives and Endpoints

Objectives	Endpoints
Primary	
To test the hypothesis that more Trained Users can successfully administer NG than GEK when treating a simulated episode of severe hypoglycemia.	The percentage of Trained Users that perform a successful administration (complete dose delivered and all critical steps completed), both for NG and GEK. See Section 5.1.3.4 for definitions of complete dose and critical steps.
Secondary	
To test the hypothesis that more Untrained Users can successfully administer NG than GEK when treating a simulated episode of severe hypoglycemia.	The percentage of Untrained Users that perform a successful administration (complete dose delivered and all critical steps completed), both for NG and GEK. See Section 5.1.3.4 for definitions of complete dose and critical steps.
To compare the average time to successfully administer NG, compared with GEK.	The time taken by Trained Users and Untrained Users to successfully administer NG or GEK (complete dose delivered and all critical steps completed), as measured by site staff.
To compare percentages of users who complete critical administration steps for both NG and GEK.	The percentages of Trained Users and Untrained Users who complete all of the critical steps for both NG and GEK, as assessed by site staff.
To assess the number of simulations that result in successful administration of NG.	The percentage of all simulations that result in a successful administration of NG, for all users combined.
To assess whether, overall, one device (NG or GEK) is preferred over the other.	The percentage of participants (Trained Users, PWDs and Untrained Users) that prefer one device over the other, as recorded in a questionnaire.
To assess overall ease of use of both devices (NG and GEK).	The 'ease of use' questionnaire ratings given to NG and to GEK by Trained Users, PWDs and Untrained Users.

Objectives	Endpoints

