5.4. Scientific Rationale for Study Design

The use of a crossover design allows a within-participant comparison of NG with GEK.

The use of 2 groups of participants, Trained User and Untrained User, is intended to simulate the types of people in the real world who are typically required to administer glucagon in an emergency: caregivers/relatives/close friends of PWDs who have received instruction in how to administer glucagon; and colleagues or acquaintances who have not received instruction, but still may be willing to step in.

The process of a PWD relaying instructions to the Trained User – rather than the Trained User receiving instruction first-hand from site staff – is intended to simulate the real-life tendency for PWDs to learn from a medical professional how to use a GEK, and to later relay this information to caregivers, relatives and/or close friends. The “memory decay” period is intended to simulate the delay that occurs in relaying these instructions.

A manikin will represent a person experiencing severe hypoglycemia; this allows for better control of the variables of each simulation, and avoids ethical issues related to the induction of severe hypoglycemia in people.

The PWD will not observe simulations in real time, so as to minimize the risk of their intervening or otherwise influencing the Trained User. This is intended to ensure simulations are like-for-like between participants and between devices, which will aid comparison.

In Part A, the manikin will appear to have the same gender as the PWD, and will be referred to with the PWD’s name, to simulate the increased stress and pressure of treating a relative or close

friend. In Part B, this is not a pertinent factor, and manikins will default to being male in appearance.

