7.1. Treatment Administered

This study involves a comparison of NG with a commercially available glucagon injection kit, administered to a manikin as part of a simulated severe hypoglycemia emergency. No treatment will be administered to humans.

The investigator or designee is responsible for

- explaining the correct use of the devices to PWDs
- verifying that the simulations are conducted properly
- maintaining accurate records of NG and GEK device dispensing and collection
- ensuring all devices are destroyed at the end of the study

7.1.1. *Packaging and Labeling*

Investigational NG devices will be provided empty of drug product, with a mock label, in shrink-wrap, and labeled per local regulations. Commercially available glucagon injection kits are labeled according to the country's regulatory requirements.

In Part A, during the demonstration given by site staff to PWDs, and the demonstrations by PWDs to their accompanying Trained User, written Instructions for Use (IFU) will be provided for both devices.

For each simulation, GEK devices will be provided sealed, and NG devices provided in shrink-wrap.

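### Section 5.1.3.3 places an insulin syringe and insulin vial within reach in the simulations, and neither document makes the vial drug-free: a small, avoidable participant-safety risk

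*Protocol*

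**What the plan says.** Protocol 5.1.3.3 describes a receptacle near the manikin that holds diabetes supplies and the assigned glucagon device. The list of supplies ends with "strips, alcohol swabs, lancing device, insulin syringe and a vial of insulin) and the glucagon device (NG or GEK depending on randomization". These contents are stated as definite, and only the additional everyday items are left optional. Sections 5.1.3.1 (Part A) and 5.1.3.2 (Part B) both refer to 5.1.3.3 for their simulations. The SAP does not mention the vial or the syringe.

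The same section sets the working conditions: "Distracting sounds and events will be incorporated to simulate the stress of a real-life situation".

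The protocol anticipates mistaken use of the insulin. Section 5.1.3.1 provides that "there will be no questionnaire for a simulation if insulin was wrongly administered instead of the glucagon device", and 5.1.3.2 has the same rule. Both schedules in Section 2 give insulin used in place of glucagon as an example of a significant error.

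For the GEK, Section 3.3 recognises a risk of "needle-stick injury, which may also result in accidental administration of the marketed comparator product". It also says that "there is no expected benefit to study participants". For the nasal glucagon (NG) device, Section 7.1.1 is explicit about content: "Investigational NG devices will be provided empty of drug product, with a mock label, in shrink-wrap".

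**The concern.** Users in both parts must be free of type 1 and type 2 diabetes (6.1, criteria 3 and 7). They work against the clock with deliberate distraction, and the plan itself allows that some will pick the insulin. Such a user may draw up insulin and hold a loaded syringe. Section 3.3 already accepts, for the GEK, that a needle-stick can deliver drug to the person holding the syringe, and the same mechanism applies to an insulin syringe.

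If the vial is active, what is at stake is an accidental insulin dose, and possible hypoglycemia, in a person who has no clinical reason to receive it and no expected benefit from the study. Nothing the study measures requires that risk.

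**Working it through.** The plan gives no figure on this point, so there is none to reproduce. The check is a reading of the text plus a count of how often the item is present.

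**What the documents establish**

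1. *Is the item specified?* Yes. Section 5.1.3.3 lists the insulin syringe and the vial without condition, whichever device is assigned, and both parts cite it.
2. *Is the vial stated to be empty, mock or filled with something else?* No, in neither document. Section 3.1 says that no drug will be given to people. That describes intended dosing and does not settle what the vial holds, since Section 3.3 still recognises accidental administration.
3. *Is mistaken use of insulin foreseen?* Yes, in Section 2 (both schedules), 5.1.3.1 and 5.1.3.2. These places describe insulin given in the simulation, that is, to the manikin. They do not describe insulin entering the user. They do imply that the user may handle it.
4. *Is this source named in the risk text?* No. Sections 3.3, 9.2 and 9.4 tie needle-stick risk to the GEK. In NG simulations the assigned product is described in 3.2 as an alternative "with a needle-free device and fewer steps for administration", and 7.1.1 says it is supplied empty. In those simulations the insulin vial is therefore the only listed source of injectable drug.
5. *Does any endpoint need active insulin?* No. Section 5.1.3.4 scores success only on the critical steps and complete dose for NG or GEK. A user who gives the vial's contents instead of the glucagon device fails whatever the vial holds. The questionnaire rules depend on which item was used, not on what it contains.

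**How often the item is present**

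Inputs are from Protocol 5.2: 26 completers per part, and planned enrollment of 39 Trained and 33 Untrained Users. Each user does one NG and one GEK simulation.

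- Completers: 26 × 2 = 52 in Part A and 26 × 2 = 52 in Part B. The total is 52 + 52 = 104 (52 NG and 52 GEK).
- Upper bound, if everyone enrolled did both simulations: 39 × 2 = 78 and 33 × 2 = 66. The total is 78 + 66 = 144.

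These figures count simulations in which the vial and syringe are in the room. They do not count handling, needle-sticks or exposures. The documents give no rate for any of those, so no expected number of events can be calculated.

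**The case against.** The strongest reply is that the hazard depends on a document we have not seen. Section 5.1.3 leaves simulation details to an operations manual, and 5.1.3.3 is headed as an example. Preparation of props is the kind of detail such a manual would hold, and it may already specify a mock vial. This stands: active insulin is not shown. It does not remove the point, because the protocol's own text names insulin without qualification.

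Exposure also needs a chain of events. The user must disregard the instruction to find the glucagon device, draw up insulin, suffer a needle-stick and receive a meaningful amount. No link has a stated frequency. This stands too, and it is why the risk is called small.

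The response to an event is largely in place. Section 2 covers accidents during simulations, the management clause in 9.2 is not limited to the GEK, and staff monitor simulations closely (9.4, written for the GEK). These measures deal with an event once it has happened. A drug-free vial prevents the insulin exposure.

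A reader might take the explicit NG wording in 7.1.1 as evidence that the insulin vial must be live, or as an inconsistency. It is neither. Section 7.1.1 covers the two compared products, and its silence on the other supplies implies nothing about their contents.

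A reader might also say that the plan contradicts its reason for using a manikin, namely that it "avoids ethical issues related to the induction of severe hypoglycemia in people". That sentence in 5.4 concerns deliberate induction and does not address accidental needle-sticks.

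Finally, a prop could alter behaviour in a study meant to resemble real life (5.1). An empty or plainly mock vial might signal that insulin is the wrong choice, or stop a user from completing the error. This objection stands, and it determines what kind of prop is needed.

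**Conclusion.** The point holds as an optional, low-cost improvement in participant safety. As written, the protocol puts an insulin syringe and an insulin vial within reach of non-diabetic users under induced stress, foresees that some will use them, and does not say the vial is drug-free.

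The conclusion rests on two assumptions: that 5.1.3.3 is followed as written, and that the operations manual does not already substitute a prop. If the manual does, the remaining gap is one of wording.

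The size of the risk cannot be stated. It would be tempting to present a fall from 104 simulations with insulin to none as the benefit of the change, but the documents do not support that. The count measures presence, it assumes an active vial, and no injury probability is given. Nor do the documents show that the sponsor chose to use live insulin.

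The primary comparison, the sample size, the power and every planned conclusion are unaffected.

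**What to change.** In Protocol 5.1.3.3, replace the insulin vial with a realistic, liquid-filled, drug-free vial (for example sterile saline) that looks like a commercial insulin vial. A user who chooses insulin in error can then still draw it up, inject it and be seen to do so, without possible exposure to insulin. An empty or visibly mock vial would not serve. If the operations manual already specifies a suitable prop, say so in the same phrase.

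The cost is one phrase and the preparation of prop vials: at most 104 for 52 completers, or 144 if all 72 enrolled users do both simulations and no vial is reused. No extra visits, participants, staff or data fields are needed. The sharps risk remains, because the syringe and lancing device stay in the room. Naming those sharps in 3.3, 9.2 and 9.4 would be a useful clarification but is not required for this change.
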